7.2. Definition of Serious Adverse Device Event (SADE)

The SADE is the adverse device effect that has resulted in any of the consequences characteristic of a serious adverse event (SAE).

The FDA definition of a SAE will be used in this study: An AE or suspected adverse reaction is considered "serious" if, in the view of either the PI or sponsor, it results in any of the following outcomes:

- Death,
- A life-threatening adverse event,
- Inpatient hospitalization or prolongation of existing hospitalization,
- A persistent or significant incapacity or substantial disruption of the ability to conduct normal life functions, or
- A congenital anomaly/birth defect.

Important medical events that may not result in death, be life-threatening, or require hospitalization may be considered serious when, based upon appropriate medical judgment, they may jeopardize the participant and may require medical or surgical intervention to prevent one of the outcomes listed in this definition. All SADEs will be reported to Medline, regardless of potential relationship to the study product(s). SADEs will be reported to the reviewing IRB as necessary according to their reporting requirements.

7.3. Definition of Unanticipated Adverse Device Effect (UADE)

Any serious adverse effect on health or safety or any life-threatening problem or death caused by or associated with a device, if that effect, problem, or death was not previously identified in nature, severity, or degree of incidence in the investigational plan or application (including a supplementary plan or

application), or any other unanticipated serious problem associated with a device that relates to the rights, safety, or welfare of the participants.

7.4. Severity of ADE

- **Grade 1:** Mild; asymptomatic or mild symptoms; clinical or diagnostic observation only; intervention not indicated.
- **Grade 2:** Moderate; minimal, local or noninvasive intervention indicated; limited age-appropriate instrumental activities of daily living.
- **Grade 3:** Severe or medically significant but not immediately life threatening; hospitalization or prolongation of hospitalization indicated; disabling; limiting activities of daily living involving self-care.
- **Grade 4:** Life threatening consequences; urgent intervention indicated
- **Grade 5:** Death related to ADE

7.5. Relatedness of ADE and SADE

- **Unrelated:** This category applies to those ADEs, which after careful consideration, are clearly and incontrovertibly due to extraneous causes (disease, environment, etc.)
- **Possible:** This category applies to those ADEs for which, after careful medical consideration at the time they are evaluated, a connection with the Investigational Product administration appears unlikely but cannot be ruled out with certainty.
- **Probable:** This category applies to those ADEs, which after careful medical consideration at the time they are evaluated, are felt with a high degree of certainty to be related to the study product(s).
- **Definite:** This category applies to those ADEs, which after careful consideration, are clearly and incontrovertibly due to the study product(s).

7.6. Expectedness

The PI will be responsible for determining whether an ADE or SADE is expected or unexpected. An ADE will be considered unexpected if the nature, severity, or frequency of the event is not consistent with the risk information previously described for the study intervention.

7.7. ADE Reporting

The ADEs will be recorded on the ADE form (provided by Medline) by the qualified designee and reviewed by the PI. Changes in the severity of an ADE will be documented to allow an assessment of the duration of the event at each level of severity. Changes in severity will necessitate a new CRF to document the new level of severity. ADEs characterized as intermittent will require documentation of onset and duration of each episode.

Non-serious ADEs will be reported to the study sponsor on a monthly basis for review or as agreed upon with the study sponsor, and reported to the IRB per IRB reporting requirements.

7.8. SADE and UADE reporting

The PI shall complete an SADE form (provided by Medline) and submit to the study sponsor as soon as possible, but in no event later than 48 hours after the PI first learns of the effect. The PI will be responsible for reporting the event to the IRB, if applicable, per the IRB's reporting requirements. The sponsor is

responsible for conducting an evaluation of the SADE, and shall report the results to the FDA and to all reviewing IRBs, if applicable, within 10 working days after the sponsor first receives notice of the effect. Thereafter, the sponsor shall submit such additional reports concerning the effect as FDA requests.

For questions regarding this process or the event, you may contact your Medline Clinical Designee or the Medline Director of Clinical Operations:

Name: [name], Director [name], BSN, CCRA
[contact]
E-mail: [contact]

8. STATISTICAL CONSIDERATIONS

8.1. Sample Size Determination

The sample size of 119 skin fold conditions was selected to detect a minimal clinically significant difference of 10 in the VAS pain scale between days of SPT changes with an estimated standard deviation of 30 and a Bonferroni adjusted α of $\alpha = .0083$ at 80% power, using the “Paired Wilcoxon Signed-Rank Test” procedure in PASS 2021 Power Analysis and Sample Size Software (2021). NCSS, LLC. Kaysville, Utah, USA, ncss.com/software/pass). It is noted that participants may have skin folds with independent skin fold conditions. One participant may be the source of, at most, two skin fold conditions for the purposes of this study. The candidate skin fold conditions must be, in the assessment of the PI or qualified designee, anatomically distant enough to permit objective assessment of discomfort (pain, itching, and burning) in each target area by the participant. In the event that a participant withdraws from the study, additional participants will be enrolled to achieve a final number of 119 target areas with complete data and until adequate power for analysis has been reached.

8.2. Randomization

No randomization is planned at this time.

8.3. Populations for Analyses

The analyses will be performed on the intent-to-treat population, which consists of all participants who were qualified for entry criteria and adhered to the protocol, meaning completing five days of treatment with complete data on assessment of skin fold conditions, as well as responses on discomfort and overall experience with the SPT.

No per protocol, safety, or other analysis groups are planned.

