5.4 Early Withdrawal and Replacement

Participants whose skin fold conditions are healed prior to Day 5 will be considered to have complete data.

Participation in the study may end at several critical points:

- Participant withdraws from the study for any reason, including when the target area(s) have not healed but the participant is discharged due to resolution of the medical condition for which the participant was hospitalized.
- Participant is not compliant with study procedures.
- Participant presents with adverse event(s) such that, in the opinion of the PI, it is in the best interest of the participant to discontinue study participation.
- Protocol violation requiring discontinuation of use of the study product(s).

Based on the above reasons, if any participant withdraws from the study or is dismissed, additional participant(s) will be recruited such that the total number of target areas included in the study will be 119.

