8.8. Missing Data

All attempts will be made to collect all data per protocol. Any data point that appears to be erroneous or inexplicable based on clinical judgement will be investigated as a possible outlier. In general, values for missing data will not be imputed unless methods of handling missing data are specified in this section or relevant sections.

For the analyses of all primary and secondary objectives, observations with missing clinical ratings (ie, rating of erythema by a third-party clinician) or self-reported ratings (ie, VAS score of participant experience) will be dropped from the analysis of variable of interest.

All missing data will be quantified in the final report and possible biases for any missing data will be reported.

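### The only analysis set is labelled intent-to-treat but admits completers only; withdrawn areas are replaced and never analysed, and the rule contradicts Section 8.8

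*Combined protocol and SAP*

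**What the plan says.** All references are to the combined protocol and SAP.

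- **Section 8.3** names one population, calls it intent-to-treat, and defines it as "all participants who were qualified for entry criteria and adhered to the protocol, meaning completing five days of treatment with complete data" on the skin fold assessments, "as well as responses on discomfort and overall experience with the SPT". It adds: "No per protocol, safety, or other analysis groups are planned".
- **Section 5.4** lists the ways participation can end: withdrawal for any reason, "including when the target area(s) have not healed but the participant is discharged due to resolution of the medical condition" that led to admission; non-compliance; adverse events; and protocol violations. Those who leave are replaced. Participants healed before Day 5 are deemed complete.
- **Section 8.1** sets the replacement target: "additional participants will be enrolled to achieve a final number of 119 target areas with complete data".
- **Section 8.8** has a different rule. It covers "observations with missing clinical ratings (ie, rating of erythema by a third-party clinician") and says that these, like missing "self-reported ratings (ie, VAS score of participant experience) will be dropped from the analysis of variable of interest". It also promises: "All missing data will be quantified in the final report and possible biases for any missing data will be reported".
- **Section 8.2** plans no randomisation, and Section 4 describes no control arm.

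**The concern.** An intent-to-treat set keeps everyone who started treatment, whatever followed. The set in Section 8.3 is conditioned on what followed: adherence, duration and completeness. An area healed by Day 3 is kept, while an area still unhealed when its participant is discharged that day is replaced. Membership therefore depends partly on the outcome being measured.

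In a single-arm study the result is the before-after change itself. There is no comparison arm in which the same selection might partly cancel, so any selection on response goes directly into the estimate. Section 8.3 does state its conditions openly. The harm is that a selected set carries the label of an unselected one, with no all-treated analysis beside it to show the difference.

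Sections 8.3 and 8.8 also cannot both be followed for the same endpoint, so two careful analysts would build different datasets. Section 7 has device events recorded for everyone, but no summary or denominator is specified and Section 8.3 rules out a safety set.

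**Working it through.** **1. The two rules side by side.** Take a participant with every skin and discomfort rating but no experience survey. Section 8.3 removes that participant from every primary endpoint. Section 8.8 removes only the missing survey value and keeps the rest. Both of Section 8.8's own examples, the erythema rating and the experience VAS, are items that Section 8.3 requires to be complete. Section 8.8 also leaves open whether an observation is one visit or a whole area.

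**2. The plan's own figure.** Inputs from Section 8.1: difference 10, SD 30, alpha 0.0083, power 80%, paired Wilcoxon test. With effect size 10/30, a two-sided paired t-test (noncentral t) needs 113. Dividing by the Wilcoxon efficiency 3/π gives 113 × π/3 = 118.3, so 119. The figure reproduces. It is a count of complete areas with no dropout allowance; replacement takes the place of one.

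**3. Treated areas left out.** The withdrawal rate *w* is an assumption. Treated areas needed for *c* complete areas = *c*/(1 − *w*).

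| *w* | Treated for 40 / 80 / 119 complete | Left out at the end: 119/(1 − *w*) − 119 |
|---|---|---|
| 5% | 42.1 / 84.2 / 125.3 | 6.3 |
| 10% | 44.4 / 88.9 / 132.2 | 13.2 |
| 20% | 50.0 / 100.0 / 148.8 | 29.8 |

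**4. Discharge unrelated to skin response.** This was simulated in 24 scenarios of 400,000 areas each. All inputs are assumed:

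- Latent start is normal with mean 2.2 and SD 0.8.
- Slope per day has mean −0.1, −0.2 or −0.3 and SD 0.1 or 0.3; visit noise has SD 0.2 or 0.5.
- Scores are rounded and clipped to 0–4, with Day 0 at least 1.
- An area heals at its first daily score of 0 and stays healed.
- Unhealed areas are discharged on Days 1–4 with probability 0.05 or 0.15 per day, before that day's assessment.

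At 0.05 per day (16–18% of areas lost) completers overstate mean improvement by at most 0.015 Likert points. At 0.15 per day (43–47% lost) the overstatement is at most 0.05 points, up to 10% of the change. A few scenarios show a slight understatement, about 0.01 at most.

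**5. Stopping that depends on response.** Assume no true VAS change, SD 30 mm, and dropout log-odds that rise by 0.5 or 1.0 per SD of worse change. The spurious gain is the completers' mean change. The false-positive rate for one contrast uses the noncentral t with n = 119 and the completers' SD (28.3–29.8 mm), ignoring the omnibus gate. The Tukey critical value for four means and 354 df is 2.58.

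| Dropout | Spurious gain, mm (0.5 / 1.0) | False positive at 0.0083 | False positive at Tukey 2.58 |
|---|---|---|---|
| 5% | 0.74 / 1.41 | 0.011 / 0.018 | 0.014 / 0.023 |
| 10% | 1.47 / 2.72 | 0.018 / 0.052 | 0.023 / 0.06 |
| 20% | 2.88 / 5.20 | 0.056 / 0.253 | 0.069 / 0.287 |

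**6. The survey requirement.** Suppose 5% of experience surveys are missing. If Section 8.1's target of 119 complete areas is met, Section 8.3 excludes 119/0.95 − 119 = 6.3 further treated areas. If only withdrawals are replaced, 0.95 × 119 = 113 areas are analysed. Section 8.8 excludes none from the primary endpoints.

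**The case against.** The strongest reply is about size. The one exit cause that Section 5.4 spells out, unhealed discharge, produces almost no bias in step 4. The larger figures in step 5 need response-dependent stopping whose rate and strength appear nowhere in the documents, and at 5% dropout the false-positive rate stays at 1–2%. This stands: step 5 is a sensitivity range, not an estimate.

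A second point is that the remedy is partial. At 20% dropout, if one earlier visit correlates 0.7 to 0.3 with the final change, an all-available-visits analysis still leaves 1.50–2.63 of 2.88 mm, or 2.80–4.78 of 5.20 mm. That also stands. The gain is largely in transparency and correct labelling.

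Third, safeguards exist. Section 8.4 has deviations reviewed and their handling decided before analysis, and Section 8.8 promises to report missing data and possible bias. Exclusion would not be silent, but neither provision puts a withdrawn area into an analysis.

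Fourth, Section 8.3 could be read as governing membership and Section 8.8 as governing variables within the set; HCP feedback is not on Section 8.3's completeness list, so Section 8.8 keeps some work. The reading fails for Section 8.8's own two examples.

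Finally, five days of treatment in Section 8.3 need not exclude early healers, since Sections 5.4 and 6.3 plainly mean to keep them. That mismatch is only a wording fix.

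**Conclusion.** The concern holds, and it rests on the text rather than the simulations. The sole analysis set is mislabelled, leaves out treated areas partly according to outcome, has no all-treated analysis beside it, and conflicts with the missing-data rule. It should be corrected before analysis.

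The size of the bias cannot be derived from the documents. It is likely small if exits are mostly ordinary discharge. It could be material if exits follow poor response: 2.9–5.2 mm at 20% dropout under the assumed slopes, against a 10 mm target. The sample-size arithmetic is sound on its own inputs and is not in question here.

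**What to change.** - **Section 8.3:** define the primary set as all target areas with SPT applied and a Day 0 assessment, analysed with the planned mixed models on all available visits. Drop the survey-completion requirement. Keep completers as a sensitivity analysis under that name. Tabulate withdrawn areas by reason, and summarise device events over all treated participants.
- **Section 8.8:** state that a missing rating drops only that visit for that variable.
- **Early healers:** include them, with the last-day assessment standing for Day 5 as the protocol already intends, and state the assumption that healing persists. An area healed on Day 1 or 2 has no Day 3 value, and Day 3 is in three of the five contrasts in Section 8.9.1. One option is to carry the healed score to Day 3 and also show the result with Day 3 missing. In the step 4 model without discharge, about 3–16% of areas are affected, and leaving them out understates Day 0 to Day 3 improvement by 0.02–0.13 points.
- **Sections 4.2, 5.4, 8.1 and 8.5:** allow replacements to be recruited, keep withdrawn areas in the analysis, and say which areas count toward 40, 80 and 119.

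The cost is wording in these sections, with no new visits. The analysed number may exceed 119 and the estimate may be less favourable. No assessment is specified at withdrawal for unhealed areas, so some will contribute few visits, and an area lost before Day 1 only its Day 0 value.

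### The plan has no safety set and no adverse device event summary, and its only analysis population leaves out anyone stopped by an adverse event

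*Combined protocol and SAP*

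**What the plan says.** Four parts of the combined protocol and SAP bear on this.

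- **Section 8.3 (Populations for Analyses).** "The analyses will be performed on the intent-to-treat population". Membership is limited to participants who met the entry criteria and "adhered to the protocol, meaning completing five days of treatment with complete data on assessment of skin fold conditions", together with responses on discomfort and experience. The section closes with: "No per protocol, safety, or other analysis groups are planned".
- **Section 5.4 (Early Withdrawal and Replacement).** Participation may end because of adverse events where, "in the opinion of the PI, it is in the best interest of the participant to discontinue study participation". Then, "if any participant withdraws from the study or is dismissed, additional participant(s) will be recruited", so that 119 target areas are included. One group that finishes early keeps its place: "Participants whose skin fold conditions are healed prior to Day 5 will be considered to have complete data".
- **Section 8.1 (Sample Size Determination).** After withdrawals, "additional participants will be enrolled to achieve a final number of 119 target areas with complete data".
- **Sections 1.2, 7 and 9.2.2.** Adverse events are monitored on every study day. ADEs go on a form that the principal investigator (PI) reviews. Non-serious ADEs reach the sponsor monthly or as agreed, and serious ones (SADEs) within 48 hours. The PI reviews all of them. None of this is restricted to completers.

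Sections 8.6 and 8.9 cover skin fold signs, odor, discomfort, moisture, provider feedback and participant experience. They contain no safety endpoint, event rate, denominator or ADE table.

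**The concern.** A safety summary needs everyone exposed in its denominator, because the people who stop early are the ones most likely to have had a problem. Here the one population for analysis is selected partly on tolerability. A participant whose reaction ends participation fails the five-day and complete-data conditions, and a newly recruited participant fills the gap. Section 2.3.1 names allergic reaction to the fabric, the hydrogen peroxide or the tape as the potential risk, and that kind of event could end participation.

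At stake is what the final report can say about safety. Section 2.3.2 notes that the textile needs no prescription and that the data may benefit consumers without clinical training. Such readers will look for an event rate. The plan gives the report's author no rule for producing one, and the only defined population is the wrong one for the purpose.

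**Working it through.** **1. What 119 counts.** The inputs in Section 8.1 are a difference of 10, SD 30, alpha 0.0083 and 80% power. A paired t-test (noncentral t, two-sided) needs n = 113. Dividing by the signed-rank test's efficiency under normality, 3/π, gives 113 × π/3 = 118.33, rounded up to 119. The plan's figure is reproduced. It carries no allowance for dropout, which fits Sections 5.4 and 8.1: 119 is the number of complete target areas, after replacement.

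**2. Where a participant stopped by an adverse event ends up.**

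| Question | Section | Answer |
|---|---|---|
| Is the event recorded and reported? | 1.2, 7.7, 7.8 | Yes |
| Is it reviewed? | 9.2.2 | Yes, by the PI |
| Is the participant in the analysis population? | 8.3 | No: five days and complete data are required |
| Does an early-finish exception apply? | 5.4 | Only for healing |
| Is the participant replaced? | 5.4, 8.1 | Yes |
| Is there another population? | 8.3 | Ruled out |
| Is an ADE summary planned on any set? | 8.6, 8.9 | No |

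**3. Direction of the bias if a rate were computed under Section 8.3.** Let n be the enrolments in the 8.3 population, m those among them with an ADE, and k the enrolments stopped by an ADE.

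- Rate on the 8.3 population: m/n
- Rate on all treated: (m + k)/(n + k)
- Difference: k(n − m)/[n(n + k)], which is positive whenever k > 0 and m < n, and zero when k = 0

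**4. Illustration.** The documents give neither m nor k, so both are assumed. Each stopped enrolment counts once, with one ADE. Since 119 counts target areas and an enrolment supplies one or two, n lies between 60 (119/2 = 59.5, rounded up) and 119. Take m = 2:

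| k | n = 119: 8.3 population | n = 119: all treated | n = 60: 8.3 population | n = 60: all treated |
|---|---|---|---|---|
| 0 | 2/119 = 1.7% | 2/119 = 1.7% | 2/60 = 3.3% | 2/60 = 3.3% |
| 3 | 1.7% | 5/122 = 4.1% | 3.3% | 5/63 = 7.9% |
| 6 | 1.7% | 8/125 = 6.4% | 3.3% | 8/66 = 12.1% |
| 12 | 1.7% | 14/131 = 10.7% | 3.3% | 14/72 = 19.4% |

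With m = 0 and k = 6, the 8.3 population shows 0%, against 6/125 = 4.8% or 6/66 = 9.1%.

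**5. Other dropouts.** The table isolates stops for an ADE. If j further enrolments leave without an ADE, for example at discharge, the all-treated rate is (m + k)/(n + k + j). It falls below m/n only if m·j > k(n − m). With n = 119, m = 2 and k = 3 that means 2j > 351, so j of at least 176. With k = 0, any such dropout lowers the all-treated rate when m > 0.

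**The case against.** The strongest reply is that no device-event rate is planned, so there is no biased rate in the plan. This is correct. A reader might infer from Section 8.3 that the ADE rate will be taken from those who tolerated the textile, or that stopped cases are struck from the study's only safety summary. The documents support neither reading, because they plan no rate and no summary. What they show is an omission, together with a population rule that would bias a rate if one were computed under it.

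Second, Section 8.3 can be read as an efficacy population, since its data requirements are the efficacy and experience assessments. That is fair. On that reading, though, ADEs have no population at all, and the section says outright that none will be added.

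Third, safety is handled elsewhere: events are monitored daily, reported to the sponsor and the IRB, reviewed by the PI, and can lead to suspension under Section 9.2.3. Replacement does not delete an event record. All of this stands, and it rules out any suggestion that events are lost. These are case-by-case duties, however, and do not say how events enter the final results.

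Fourth, a reader might go further on size. Suppose five participants stop for a skin reaction and no completer has one. The all-treated estimate is 5/124 = 4.0% (exact 95% interval 1.3% to 9.2%), against 0/119 with an upper limit of 3.1%. It is tempting to say that the completer figure excludes the true rate. It does not follow: the five events are assumed, 4.0% is an estimate, and the two intervals overlap. The sum also assumes one target area per participant. With two each it becomes 5/65 = 7.7% against 0/60.

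Finally, the minimal-risk statement in Section 2.3.3 is a judgement made before the study. It is not a result drawn from the 8.3 population and is no evidence of harm from it.

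**Conclusion.** The point holds as a gap in the safety plan. Participants dismissed for an adverse event fall outside the only analysis population and are replaced. No safety set is allowed, and no ADE summary or denominator is specified. An event rate computed on the 8.3 population would omit ADE-related discontinuations and be biased low by that omission.

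The size cannot be estimated from the documents. It is zero if nobody stops for an ADE. Under the assumed counts in the first table row with k > 0 it is 2.4 percentage points (4.1% less 1.7%) with 119 enrolments, and 4.6 (7.9% less 3.3%) with 60. The illustration assumes that each stop is for one ADE; Section 5.4 speaks of adverse events generally, and some may be unrelated to the textile.

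The change should be made, but the primary efficacy test does not depend on it.

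**What to change.** Replace the last sentence of Section 8.3 with wording such as:

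> Safety set: all participants with at least one SPT application. ADEs and SADEs, including those leading to dismissal, are summarised on this set per person (linking re-enrolment IDs), with exact 95% intervals.

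Add the matching table to Section 8.9. Linking is needed because Sections 5 and 6.1.2 allow a person to re-enter under a new ID; the master list in Section 9.2.1 should make it feasible. Add a summary per treated target area only if the ADE form identifies the area, which Section 7.7 does not say.

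While editing Section 8.3, reconcile its five-day requirement with Section 5.4, which counts early healers as complete.

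The cost is one sentence and one extra table. The per-person summary uses events already recorded under Section 7 and changes neither the sample size nor any study procedure. The downside for the sponsor is that the reported event rate may be less favourable.
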